1.1 Objectives and Estimands/Endpoints

The estimands corresponding to the analysis of the primary and secondary objectives are described below:

Table 1-1: Objectives and Estimands/Endpoints

Objectives	Estimands / Endpoints
Primary Efficacy Objective	
To evaluate the efficacy of Zilucoplan over placebo in creatinine kinase (CK) levels in participants with IMNM	
Primary Estimand:
 
• Treatment: Zilucoplan administered by daily subcutaneous (SC) injection (0.3 mg/kg) vs matching placebo• Target Population: is defined through the inclusion/exclusion criteria at Sections 8.1 and 8.2 of the study protocol reflecting the targeted IMNM population• Endpoint: Percent change from Baseline to Week 8 in CK levels;• Intercurrent event (ICE) handling: regardless of any treatment discontinuation for any reason; censoring after prohibited medication;• Population level summary: difference in ranks of the percentage change from Baseline between treatment conditions followed by the Wilcoxon-Mann-Whitney odds (WMWodds) and Hodges–Lehmann estimator.

Table 1-1: Objectives and Estimands/Endpoints

Objectives	Estimands / Endpoints
Primary Safety Objective	
To evaluate the safety Zilucoplan over placebo in creatinine kinase (CK) levels in participants with IMNM	
Primary Safety Endpoint:
 
Incidence of Treatment-emergent Adverse Events
Secondary Efficacy Objective	
To further evaluate the efficacy of Zilucoplan over placebo in participants with IMNM	
Secondary Estimands:
 
Treatment: Zilucoplan administered by daily subcutaneous (SC) injection (0.3 mg/kg) vs matching placeboTarget Population: is defined through the inclusion/exclusion criteria at Sections 8.1 and 8.2 of the study protocol, reflecting the targeted IMNM populationEndpoints:
At least minimal response based on the American College of Rheumatology/European League Against Rheumatism (ACR/EULAR) Response Criteria Scale at Week 8;Change from Baseline to Week 8 in Triple Timed Up and Go (3TUG) Test (in ambulatory patients only);Change from Baseline to Week 8 in Proximal Manual Muscle Testing (MMT);Change from Baseline to Week 8 in Physician Global Activity Visual Analogue Scale (VAS);Change from Baseline to Week 8 in Patient Global Activity Visual Analogue Scale (VAS);Change from Baseline to Week 8 in Health Assessment Questionnaire (HAQ);Change from Baseline to Week 8 in MDAAT Extramuscular Disease Activity VAS Score;Change from Baseline to Week 8 in FACIT-Fatigue Scale.Intercurrent event (ICE) handling: regardless of any treatment discontinuation for any reason; censoring after administration of prohibited medicationPopulation level summary:

Table 1–1: Objectives and Estimands/Endpoints

Objectives	Estimands / Endpoints
	
– Odds Ratio (OR) of ACR/EULAR ≥ 20 response proportion between treatment conditions;– Difference in continuous endpoint means, between treatment conditions.
Other Safety Objective	
To further evaluate the safety of Zilucoplan over placebo in participants with IMNM	
Other Safety Endpoints
 
• Change in clinical laboratory tests• Change in ECG parameters• Change in vital signs parameters• Presence of Anti-Drug Antibodies
Exploratory Objectives	
To assess the long-term efficacy of Zilucoplan	
• At least minimal response based on the American College of Rheumatology/European League Against Rheumatism (ACR/EULAR) Response Criteria Scale at each visit following Week 8;• Change from Baseline of Timed Up and Go (3TUG) Test (in ambulatory patients only) at each visit following Week 8;• Change from Baseline of Proximal Manual Muscle Testing (MMT) at each visit following Week 8;• Change from Baseline of Physician Global Activity Visual Analogue Scale (VAS) at each visit following Week 8;• Change from Baseline of Patient Global Activity Visual Analogue Scale (VAS) at each visit following Week 8;• Change from Baseline of Health Assessment Questionnaire (HAQ) at each visit following Week 8;• Change from Baseline of MDAAT Extramuscular Disease Activity VAS Score at each visit following Week 8;• Change from Baseline of FACIT-Fatigue Scale at each visit following Week 8;
To assess the PK Zilucoplan	Plasma concentrations of Zilucoplan and its major metabolites
To assess the PD of Zilucoplan	
• Sheep red blood cell (sRBC) lysis assay for evaluation of classical complement pathway activation

Table 1–1: Objectives and Estimands/Endpoints

Objectives	Estimands / Endpoints
	
• Complement component 5 (C5) levels
To assess the effect of Zilucoplan on biomarkers	Mechanistic biomarkers [e.g., complement fixation, complement function, complement pathway proteins, autoantibody characterization (titer and immunoglobulin class), myocyte markers, and inflammatory markers].
To assess the effect of Zilucoplan on pharmacogenomics	Pharmacogenomic analyses (optional): Genomic studies [e.g., deoxyribonucleic acid (DNA) sequencing, including exploration of whether specific genomic features correlate with response or resistance to study drug], may be performed.

1.2 Study design

IMNM01 is a multicenter, randomized, double-blind, placebo-controlled parallel study to evaluate the safety, tolerability and efficacy of Zilucoplan in IMNM cases who are positive for anti-HMGCR (3-hydroxy-3-methyl-glutaryl-coenzyme A reductase) or anti-SRP (signal recognition particle) autoantibodies.

The planned enrollment is approximately 24 participants.

Participants are randomized at Day 1 to 1:1 ratio in order to receive:

- daily SC doses of 0.3 mg/kg Zilucoplan (12 participants), or
- matching placebo administered SC (12 participants).

Randomization is stratified based on the antibody status (anti-HMGCR+ versus antiSRP+).

Following in-clinic education and training all participants will self-inject daily SC doses of blinded study drug, according to randomized treatment allocation, for the subsequent 8 weeks. Single use pre-filled syringes in injection devices are provided for use during the study.

All standard of care therapy medications for IMNM should be kept at the same doses throughout the study, including corticosteroids, immunosuppressive drugs, and IVIG.

The study is comprised of the Main Portion and the Extension Portion. The Main Portion of the study includes a Screening Period of up to 4 Weeks and an 8 Week Treatment Period.

During the Treatment Period, participants will return to the clinic at Week 1, Week 2, Week 4 and Week 8 for safety, tolerability and efficacy evaluations.

Efficacy assessments include Creatine Kinase (CK) levels, as well as performance outcomes, clinician-reported outcomes and patient-reported outcomes (PRO).

Safety assessments include physical examination, vital signs, electrocardiogram (ECG), clinical laboratory tests, adverse event (AE) monitoring and immunogenicity.

Additional assessments include biomarker testing, pharmacokinetics, pharmacodynamics, and optional pharmacogenomics.

At the end the study Treatment Period, participants have the option to receive Zilucoplan in the Extension Portion of the study provided they meet the Extension Portion selection criteria. Visits during the first 8 Weeks of the Extension Portion are identical to the Main Portion of the study for all participants to ensure appropriate monitoring of participants transitioning from placebo to active treatment.

The study remains double-blinded until after the data from the Week 8 Main Portion have been reviewed, locked and unblinded. If a participant permanently discontinues study treatment prior to Week 8 visit for any reason, he/she will not be eligible for the Extension Portion. For participants who permanently discontinue treatment with study drug, a Safety Follow-up Visit is performed 40 days after the last dose to collect information on any ongoing AEs or new SAEs since last visit.

Schedule of Assessments at [Table 1–2](#) and [Table 1–3](#) illustrate the time and events schedule for the Main Portion and the Extension Portion of the study.

REDACTED COPY
This document cannot be used to support any marketing authorization application and any extensions or variations thereof.

Table 1-2: Schedule of Assessments During the Main Portion of the Study

Study Procedure			Week 1	Week 2	Week 4	Week 8	Safety Follow-up Visit (last dose + 40d)
	Screening Days -28 to -1	Day 1 (Baseline)	Day 8 (±2 days)	Day 15 (±2 days)	Day 29 (±2 days)	End of Main ^a Study Day 57 (±7 days)	
Informed consent ^b	X						
Review eligibility ^b	X						
Randomization		X					
Medical history ^c and demographics	X						
Height ^d and weight	X				X	X	
Prior and concomitant medications ^e	X	X	X	X	X	X	X
Safety							
Physical examination	X	X	X	X	X	X	X
Vital signs ^f	X	X	X	X	X	X	X
12-lead ECG	X					X	
Neisseria meningitidis vaccination ^g	X						
Prophylactic antibiotics ^g (if applicable)		X	X	X			
Hematology / Chemistry / CK ^h	X	X	X	X	X	X	
Coagulation ^{h, i}	X	X	X	X	X	X	
Urinalysis ^h	X	X	X	X	X	X	
Pregnancy test ^j	X	X	X	X	X	X	X
Adverse Events ^k	X	X	X	X	X	X	X ^k
Anti-Drug Antibody ^h	X		X		X	X	
Efficacy							

Table 1-2: Schedule of Assessments During the Main Portion of the Study

Study Procedure			Week 1	Week 2	Week 4	Week 8	Safety Follow-up Visit (last dose + 40d)
	Screening Days -28 to -1	Day 1 (Baseline)	Day 8 (±2 days)	Day 15 (±2 days)	Day 29 (±2 days)	End of Main ^a Study Day 57 (±7 days)	
3TUG ^{l, m}	X	X			X	X	
Proximal MMT ^l	X	X			X	X	
Physician Global Activity VAS ^l	X	X			X	X	
Patient Global Activity VAS ^l	X	X			X	X	
HAQ ^l	X	X			X	X	
MDAAT ^l	X	X			X	X	
FACIT-Fatigue ^l	X	X			X	X	
Pharmacokinetic / Pharmacodynamic							
Zilucoplan plasma PK ⁿ		X	X	X	X	X	
Pharmacodynamic analysis ⁿ		X	X	X	X	X	
Exploratory							
Autoantibodies testing ^o	X	X			X	X	
Biomarker testing ^p		X	X	X	X	X	
Pharmacogenomic analysis (optional) ^q	X	X					
Study Drug							
Zilucoplan or placebo administration ^r		X	X	X	X	X	

^a If a subject permanently discontinues study drug prior to completion of the Day 57 visit during the Main Portion, the subject should return to clinic for an End of Main Visit. If a participant consents to the Extension Portion, please see Table 1-3 for Day 57/E1 assessments. If a subject permanently discontinues study drug treatment prior to the Week 8 visit for any reason, he/she will not be eligible for the Extension Portion. For subjects who permanently discontinue treatment with study drug, a Safety Follow-up Visit will be performed at 40 days after the last dose to collect information on any ongoing AEs or new SAEs since the last study visit.

^b Procedures performed as standard of care during the Screening Period may be used to determine eligibility. Informed consent must be obtained prior to performing any study-specific procedures that are not standard of care. Eligibility must be established prior to randomization on Day 1.

^c Screening includes a detailed history of IMNM diagnosis information and local serology for anti-HMGCR or anti-SRP autoantibodies from a reputable laboratory.

^d Height will be measured only at Screening

^e All prescriptions and over-the-counter medications taken during the 30 days prior to Baseline (i.e., Day 1) through the last study visit will be documented. NOTE: A complete history of all medication taken for the treatment of IMNM will be collected.

^f The vital signs assessment will include measurement of HR, body temperature, and blood pressure in the sitting position.

^g To reduce the risk of meningococcal infection (*Neisseria meningitidis*), all subjects must be vaccinated against meningococcal infections (with a quadrivalent vaccine and, where available and in accordance with local standard of care, serogroup B vaccine) within 3 years prior to, or at the time of, initiating study drug. Subjects who initiate study drug treatment less than 2 weeks after receiving a meningococcal vaccine must receive treatment with appropriate prophylactic antibiotics (e.g., ciprofloxacin, erythromycin, penicillin V) until at least 2 weeks after initial dose of vaccine(s). Booster vaccinations should be administered in accordance with local standard of care. NOTE: In participants who received rituximab more than 90 days but less than 6 months prior to Baseline, prophylactic antibiotics (e.g., ciprofloxacin, erythromycin, penicillin V) should be given upon initiation of study drug until 6 months after the last rituximab dose.

^h All laboratory samples should be obtained prior to administration of study drug at applicable visits.

ⁱ Coagulation tests should be performed only in subjects who are receiving anticoagulant therapy.

^j For all female subjects of childbearing potential, a negative serum pregnancy test must be documented at Screening. All other pregnancy tests will be performed via urine.

^k All AEs and SAEs should be monitored until resolution or stabilization. SAEs that occur within 40 days after the last dose of study drug should be reported using the procedures outlined in the protocol. Participants will attend a clinic visit 40 days after their last dose to gather information on ongoing AEs and report any new SAEs since the last study visit. Only SAEs are collected during the screening period.

^l The clinical assessments should be performed at approximately the same time of day (preferably in the morning) and should be administered in the same order by the same well-trained evaluator (e.g., neurologist, physical therapist, or other study staff) at each visit throughout the study.

^m 3TUG will only be completed in subjects who are ambulatory.

ⁿ Blood samples for PK and PD analysis will be obtained prior to administration of study drug (within 1 hour of dosing).

^o Confirmatory serology testing for anti-HMGCR or anti-SRP autoantibodies will be done at a central laboratory.

^p Blood samples for biomarker testing will be obtained prior to administration of study drug (within 1 hour of dosing).

^q The pharmacogenomic sample may be collected at any study visit.

^r Dosing on study visit days should be held until clinical assessment and blood collection has been completed.

Table 1-3: Schedule of Assessments During the Extension Portion of the Study

	Month 2			Month 3	Month 4	Month 5	Month 6	Visits after Day E117			
Study Procedure	Day E1 ^a (Day 57)	Day E8 (±2 days)	Day E15 (±2 days)	Day E29 (±2 days)	Day E57 (±2 days)	Day E87 (±7 days)	Day E117 (±7 days)	Each Month (±7 days)	Every 3 Months (±7 days)	Final Extension Visit ^b	Safety Follow-up Visit (last dose + 40d)
Informed consent	X										
Review eligibility and randomization	X										
Weight	X			X	X		X		X	X	
Prior and concomitant medications	X	X	X	X	X	†	X	X	X	X	X
Safety											
Physical examination	X	X	X	X	†		X		X	X	X
Vital signs ^c	X	X	X	X	X		X		X	X	X
12-lead ECG	X				X				X		
Neisseria meningitidis vaccination ^d	X	Standard of Care	Standard of Care	Standard of Care	Standard of Care	Standard of Care	Standard of Care	Standard of Care			
Hematology / Chemistry / CK ^e	X	X	X	X	X		X		X	X	
Coagulation ^{e,f}	X	X	X	X	X		X		X	X	
Urinalysis ^e	X	X	X	X	X		X		X	X	
Pregnancy test ^g	X	X	X	X	X	X	X	X	X	X	X
Adverse Events ^h	X	X	X	X	X	X	X	X	X	X	X ^h
Anti-Drug Antibody ^e	X	X		X	X		X		X	X	
Efficacy											

Table 1-3: Schedule of Assessments During the Extension Portion of the Study

	Month 2			Month 3	Month 4	Month 5	Month 6	Visits after Day E117			
Study Procedure	Day E1 ^a (Day 57)	Day E8 (±2 days)	Day E15 (±2 days)	Day E29 (±2 days)	Day E57 (±2 days)	Day E87 (±7 days)	Day E117 (±7 days)	Each Month (±7 days)	Every 3 Months (±7 days)	Final Extension Visit ^b	Safety Follow-up Visit (last dose + 40d)
3TUG ^{i,j}	X			X	X		X		X	X	
Proximal MMT ⁱ	X			X	X		X		X	X	
Physician Global Activity VAS ⁱ	X			X	X		X		X	X	
Patient Global Activity VAS ⁱ	X			X	X		X		X	X	
HAQ ⁱ	X			X	X		X		X	X	
MDAAT ⁱ	X			X	X		X		X	X	
FACIT-Fatigue ⁱ	X			X	X		X		X	X	
Pharmacokinetic / Pharmacodynamic											
Zilucoplan plasma PK ^k	X	X	X	X	X		X		X	X	
Pharmacodynamic analysis ^k	X	X	X	X	X		X		X	X	
Exploratory											
Autoantibodies testing	X			X	X		X		X	X	
Biomarker testing ^l	X	X	X	X	X		X		X	X	
Study Drug											
Zilucoplan or placebo administration ^m	X	X	X	X	X	X	X	X	X	X	

^a For participants that decide and are eligible to continue in the Extension Portion of the study, the Day 57 visit from the Main Portion will serve as the Day E1 visit and will also include review of eligibility to continue and signing of an informed consent for the Extension Portion.

administered in the same order by the same well-trained evaluator (e.g., neurologist, physical therapist, or other study staff) at each visit throughout the study.

^b If a participant discontinues study drug treatment at any time during the Extension Portion, the participant should return to clinic for a Final Extension Visit.

^c The vital signs assessment will include measurement of HR, body temperature, and blood pressure in the sitting position.

^d During the Extension Portion of the study, all participants should have *Neisseria meningitidis* booster vaccinations as indicated by standard of care. Participants should bring their patient safety card to every study visit. If a participant does not bring the card, then a new one will be given to him/her.

^e All laboratory samples should be obtained after clinical assessments and prior to administration of study drug at applicable visits.

^f Coagulation tests should be performed only in subjects who are receiving anticoagulant therapy.

^g Urine pregnancy tests will be conducted in female subjects of childbearing potential.

^h All AEs and SAEs should be monitored until resolution or stabilization. SAEs that occur within 40 days after the last dose of study drug should be reported using the procedures outlined in the protocol. Participants will attend a clinic visit 40 days after their last dose to gather information on ongoing AEs and report any new SAEs since the last study visit.

ⁱ The clinical assessments should be performed at approximately the same time of day (preferably in the morning) and should be administered in the same order by the same well-trained evaluator (e.g., neurologist, physical therapist, or other study staff) at each visit throughout the study.

^j 3TUG will only be completed in subjects that are ambulatory.

^k Blood samples for PK and PD analysis will be obtained prior to administration of study drug (within 1 hour of dosing).

^l Blood samples for the exploratory tests will be obtained prior to administration of study drug (within 1 hour of dosing).

^m Dosing on study visit days should be held until clinical assessment and blood collection has been completed.

2 STATISTICAL HYPOTHESES

The hypotheses to be included in the testing strategy are listed at the next sections; type 1 error will be set such that a family wise type 1 error of 5% is maintained.

The primary hypothesis H_{01} will be tested at 2-sided $\alpha=5\%$. Should H_{01} is rejected then the whole α will be passed to the next hypothesis until all hypotheses are rejected. Of note, the level of a rejected hypothesis should only pass on the next testing only if the treatment effect is in favour of Zilucoplan.

2.1 Primary endpoint

The Null Hypothesis for the primary endpoint is that there is no treatment difference in Week 8 between Zilucoplan and placebo treatment conditions in the percentage change from baseline of CK levels.

The Null Hypothesis (H_{01}) asserts that it is equally likely to one treatment group to be less than or greater than the other splitting ties evenly:

Let Y_1 and Y_2 be observations drawn independently from the two IMP (Investigational Medicinal Products) distributions.

Then:

- H_{01} : $\pi = 0.5$ for both strata, where $\pi = \text{Prob}(Y_1 < Y_2) + 1/2 \text{ Prob}(Y_1 = Y_2)$ and
- H_{A1} : $\pi_i \neq 0.5$ for at least one stratum (Alternative Hypothesis)

Converting π to an odds measure: $WMWodds = \pi / (1 - \pi)$ the H_{01} and H_{A1} can be re-written as:

- H_{01} : $WMWodds = 1$
- H_{A1} : $WMWodds \neq 1$

2.2 Secondary endpoints

$H_{02.1}$: Zilucoplan is not different to placebo regimen with respect to the proportion of patients achieving at least minimal response based on the ACR/EULAR Response Criteria Scale

$H_{02.2}$: Zilucoplan is not different to placebo regimen with respect to change from baseline in Triple Timed Up and Go (3TUG) Test to Week 8 among ambulatory patients

$H_{02.3}$: Zilucoplan is not different to placebo regimen with respect to change from baseline to Week 8 in Proximal Manual Muscle Testing (MMT)

$H_{02.4}$: Zilucoplan is not different to placebo regimen with respect to change from baseline to Week 8 in Physician Global Activity Visual Analogue Scale (VAS)

$H_{02.5}$: Zilucoplan is not different to placebo regimen with respect to change from baseline to Week 8 in Patient Global Activity VAS

H_{02.6}: Zilucoplan is not different to placebo regimen with respect to change from baseline to Week 8 in Health Assessment Questionnaire (HAQ)

H_{02.7}: Zilucoplan is not different to placebo regimen with respect to change from baseline to Week 8 in MDAAT VAS Score in the Extramuscular Disease Activity item

H_{02.8}: Zilucoplan is not different to placebo regimen with respect to change from baseline to Week 8 in FACIT-Fatigue Scale

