5.4.4 Sensitivity analysis

No sensitivity analysis to be performed.

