5.4.5 Supplementary analyses

Analysis mentioned at Section 5.4.3 will be repeated in ITT with missing values imputed based on the LOCF approach from the previous non missing visit of Week 8. Based on this approach, the elements of ACR/EULAR will also be imputed with the last non missing parameter in order the score to be calculated at Week 8.

Analysis mentioned at Section 5.4.3 will be repeated in the ITT_{NOCOVID-19}. In case of non-convergence, only the summary statistics will be reported.

Analysis mentioned at Section 5.4.3 will be repeated in the PPS.

Estimand:

- Treatment: Zilucoplan administered by daily subcutaneous (SC) injection (0.3 mg/kg) vs matching placebo
- Target Population: is defined through the inclusion/exclusion criteria at Sections 8.1 and 8.2 of the study protocol reflecting the targeted IMNM population
- Endpoints:
 - ACR/EULAR of at least minimal response at Week 4;
 - ACR/EULAR ordinal treatment response at Week 4 and Week 8;
 - ACR/EULAR Total Improvement Score at Week 4 and Week 8;
 - Change from Baseline to Week 4 in Triple Timed Up and Go (3TUG) Test (in ambulatory patients only);
 - Change from Baseline to Week 4 in Proximal Manual Muscle Testing (MMT);
 - Change from Baseline to Week 4 in Physician Global Activity Visual Analogue Scale (VAS);

- Change from Baseline to Week 4 in Patient Global Activity Visual Analogue Scale (VAS);
- Change from Baseline to Week 4 in Health Assessment Questionnaire (HAQ);
- Change from Baseline to Week 4 in MDAAT Extra muscular Disease Activity VAS Score;
- Change from Baseline to Week 8 in FACIT-Fatigue Scale;
- Intercurrent event: regardless of treatment discontinuation for any reason; censoring after administration of prohibited medication;
 - Population level summary: Odds Ratio (OR) of ACR/EULAR ≥ 20 response proportion between treatment conditions (analysis will be performed as mention Section 5.4.3).
 - Population level summary: ACR/EULAR ordinal treatment response proportion in treatment conditions;
 - Difference in continuous endpoint means between treatment conditions (analysis will be performed as mention Section 5.4.3).

For the determination of ACR/EULAR response categories, see Section 6.1.5.7. Ordinal ACR/EULAR treatment response (no improvement, minimal improvement, moderate improvement, major improvement) at Week4 and Week 8 will be only be summarized by IMP.

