6.1.5 Data derivation rules

6.1.5.1 Triple timed up and go test

The triple timed up and go test (3TUG) is a non-invasive and reproducible measure, which measures clinically important muscle weakness that impairs participant's ability to walk, climb stairs and stand up from a chair. The test will only be performed in participants who are ambulatory. The 3TUG test involves the participant getting up from a seated position in a chair, walking at their normal pace for 3 meters, turning around, walking back to the chair, and sitting down. This sequence is repeated 3 times without rest. Sites will record each lap time rounded to the nearest second, and the 3TUG time is the average of the 3 lap times. The average of the 3 lap times will be calculated to the nearest tenth place (Sanders, et al. 2018). If 2 or more of the lap times are missing, the 3TUG time will be set to missing.

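### No planned 3TUG analysis scores loss of ambulation as a bad outcome: the main and per-protocol analyses omit the participant and LOCF substitutes an earlier walking time

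*SAP*

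**What the plan says.** - **Place in the sequence.** SAP 2 tests the hypotheses in fixed order so that "type 1 error will be set such that a family wise type 1 error of 5% is maintained"; after each rejection the whole alpha "will be passed to the next hypothesis until all hypotheses are rejected". CK is H01, ACR/EULAR minimal response H02.1 and 3TUG H02.2. H02.3 to H02.8 follow.
- **Population.** H02.2 is stated "with respect to change from baseline in Triple Timed Up and Go (3TUG) Test to Week 8 among ambulatory patients".
- **Who is tested.** The footnote to the Main Portion schedule in SAP 1.2 says "3TUG will only be completed in subjects who are ambulatory", and SAP 6.1.5.1 says "The test will only be performed in participants who are ambulatory". Neither gives the time at which ambulatory status is judged.
- **Missing rule.** SAP 6.1.5.1: "If 2 or more of the lap times are missing, the 3TUG time will be set to missing". No score is assigned for inability.
- **Main analysis.** SAP 5.1 and 5.4.3 plan an observed-case linear mixed model on change to Week 8, with treatment, strata and baseline. Values are censored only after prohibited medication.
- **Other analyses.** SAP 5.4.4: "No sensitivity analysis to be performed". SAP 5.4.5 repeats the model in ITT with the "LOCF approach from the previous non missing visit of Week 8", in the No-COVID-19 set and in the PPS, and adds change to Week 4.
- **Contrast with CK.** SAP 5.1.1.8.1 and 5.3.3 impute missing Week 8 CK at an extreme unfavourable value if at least 15% of participants are not evaluable. 3TUG has no counterpart.

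**The concern.** For a timed walking test, becoming unable to do it is the worst result. If that result is recorded as missing, the Week 8 comparison is between those still able to walk, and the number who are not may differ by arm.

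If placebo loses more walkers, the plan understates a benefit. If zilucoplan loses more, it overstates one. Either way the result decides whether six further hypotheses are formally tested. Protocol 5.1 describes a disease that can progress quickly to disabling atrophy, so the case is not fanciful. The missing-lap rule widens it a little: someone too weak to finish more than one of the three laps is also simply missing.

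**Working it through.** **1. Following one participant through the plan.** Take someone who walks at Baseline and Week 4 but cannot do the test at Week 8.

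| Analysis | Treatment of this participant |
|---|---|
| Main model, ITT observed case (5.4.3) | No Week 8 value; left out |
| PPS and No-COVID-19 repeats (5.4.5) | Same model, same omission |
| ITT with LOCF (5.4.5) | Kept, with the Week 4 walking time |
| Change to Week 4 (5.4.5) | Kept, with the Week 4 walking time |
| Sensitivity analysis (5.4.4) | None |

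Week 4 is the only scheduled post-baseline 3TUG before Week 8, so the LOCF value comes from a time when the participant could walk. It may already show decline. It would equal no change only if Week 4 were also missing and the Baseline value were carried. No row scores the loss of walking.

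**2. The plan's own figure.** The only power statement is for CK (about 95%). It reproduces at 94.9% with an exact Wilcoxon test, but says nothing about 3TUG. Everything below rests on assumed inputs.

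**3. Effect of one loss on the rank scale.** Start from equality and let 1 of 12 placebo participants take the worst rank:
- Probability that a zilucoplan participant does better = 0.5 × 11/12 + 1/12 = 0.542
- WMWodds = 0.542 / (1 − 0.542) = 1.18, against 1.00 at equality

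**4. Losses unrelated to the walkers' times.** Assumed: 12 per arm, SD of change 2 s, true benefit 2 s among walkers, each participant losing ambulation independently. The table compares an observed-case t-test with a Wilcoxon test giving losses the worst rank. Entries are the share of simulated trials significant at two-sided 0.05 in favour of zilucoplan.

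| Losses | Observed case | Worst rank |
|---|---|---|
| None | about 66% | about 62% |
| Zilucoplan 1/12 (one expected), placebo none | about 63% | about 37% |
| Placebo 10%, zilucoplan none | about 61% | about 68% |

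Repeat runs move these by a point or two. The first row shows that about 4 points (66 − 62) separate the two tests before anyone is lost, so only differences beyond that reflect how losses are handled.

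**5. Losses as the tail of the same decline.** Assumed: a true benefit of 0.8 SD, with participants above a fixed threshold of worsening unable to walk. About 0.4 of 12 on zilucoplan and 1.9 of 12 on placebo are then lost.

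| Analysis | Mean difference (SD) | Power |
|---|---|---|
| All participants, no loss | 0.79 | – |
| Observed case | 0.58 | 0.32 |
| LOCF | 0.70 | 0.44 |
| Worst rank | – | 0.42 |

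Here the observed-case analysis is conservative. LOCF recovers much of the difference without recording that anyone stopped walking.

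**The case against.** The strongest reply has four parts.

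- **Other measures see the decline.** MMT, the HAQ walking section (unable scores 3), both global VAS scales and, through them, ACR/EULAR can move. Clinically significant examination findings after Day 1 are recorded as adverse events (Protocol 10.2.1), and persistent disability is a seriousness criterion (Protocol 11.1.2). This stands. A reader might infer that the worst outcome vanishes from the whole evaluation, or that harm could go unseen. The documents do not support that: the gap is confined to 3TUG. The cover is partial, because ACR/EULAR scores worsening the same as no improvement, and MMT, the VAS scales and HAQ come after 3TUG in the sequence.
- **Ambulatory may mean at Baseline.** SAP 6.1.1 lists ambulatory status as a baseline characteristic. This stands too. A reader might infer that the population is selected visit by visit after randomisation, but the SAP never says so; the timing is undefined. Even on the baseline reading, someone who later cannot walk has no Week 8 value.
- **Loss is unlikely.** Protocol 5.4.2 says entrants have stable disease, and treatment doses must have been stable for 30 days. This stands and limits the importance of the point.
- **Worst-rank scoring targets a different quantity** from the stated difference in means. True, which is why it belongs in a sensitivity analysis and not in place of the main model.

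**Conclusion.** The point holds, limited to 3TUG: as written, no 3TUG analysis counts loss of ambulation as a bad outcome, and the SAP leaves the timing of ambulatory status open. Omission at Week 8 is inferred from the ambulatory-only rule combined with observed-case analysis; it is not stated.

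The direction is not fixed. The plan is conservative if placebo loses more walkers and favours zilucoplan if zilucoplan does. The size cannot be established from the documents, and the percentages above are illustrations on assumed inputs. A larger gap can be produced by assuming 20% lost on zilucoplan and none on placebo (about 58% against 14%), but nothing in the documents makes so lopsided a pattern likely, and it should not be read as the expected effect.

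Two further readings go too far. LOCF does not drop the participant or, normally, count them as unchanged. And 3TUG is third in the testing sequence, second only among the secondary endpoints. What remains is a real but modest gap that should be closed because closing it is cheap.

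**What to change.** 1. In SAP 2.2 and 5.4, define the 3TUG population as participants ambulatory at Baseline.
2. Keep the planned mixed model as the main analysis.
3. In SAP 5.4.4, for 3TUG only, replace the statement that no sensitivity analysis is planned with one Van Elteren analysis of change to Week 8. Participants unable to do the Week 8 test because of weakness share the worst rank; values missing for other reasons, such as a missed visit, do not.
4. Report by arm the number ambulatory at Baseline who could not do the test at Week 8.

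The cost is SAP wording and one extra table, using a test already planned for CK. Sample size, visits and the primary analysis do not change. The reason for a missing Week 8 3TUG must be known; if it is not already captured, it should be settled in blinded review. The downside is that the added result is on a rank scale, not in seconds, and addresses a composite estimand and not the difference in means.
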